## PLANNED SURGERY FOR LUNG CANCER:

The group that is to be operated on for lung cancer is informed about the project when visiting the Clinic for Lung Cancer Investigation. Conversation that takes place in a private room. Written information is provided. The day before surgery, when the patients routinely meet for the last interviews before surgery, written consent is secured. On these days, there will be the possibility of a follow-up interview with the possibility of the participation of co-chairs. The reflection time will thus be > 1 day.

Lung cancer investigation visit: Informed by doctor. Delivery of participant information

The day before lung cancer surgery: Additional information if desired, with co-owners. Completing informed consent.

## PLANNED SURGERY FOR ESOPHAGEAL CANCER:

The group that is to be operated on for oesophageal cancer is informed about the project when visiting the Cardiopulmonary Surgery Clinic. Conversation that takes place in a private room. Written information is provided. The day before surgery, when the patients routinely meet for the last interviews before surgery, written consent is secured. On these days, there will be the possibility of a follow-up interview with the possibility of the participation of co-chairs. The reflection time will thus be > 1 day.

Pre-study cardiopulmonary surgery: Informed by doctor. Delivery of participant information

The day before esophageal cancer surgery: Additional information if desired, with co-owners. Completing informed consent.

## SURVEYS

## STUDY 1:

In study 1, 1 lung function examination, 1 complete ultrasound examination and 1 x-ray examination are carried out.

## STUDY 2:

In study 2, only lung function examination and ultrasound examination are carried out. These are made

Lung cancer: 1) the day before surgery, 2) 3 days after surgery and 3) 2 weeks after surgery.

Oesophageal cancer: 1) the day before surgery, 2) 3 days after surgery and 3) 10 days after surgery (after which most are discharged).

LVAD implantation: 1) the day before surgery, 2) 14 days after surgery and 3) 3 months after surgery.

Heart transplant: 1) in close relation to the write-up on the heart transplant list, 2) 14 days after the operation and 3) 3 months after the operation

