## STUDY 2:

The etiology of shortness of breath is multifactorial, and shortness of breath can be a symptom of a wide range of lung or heart diseases. In failing heart pump function, shortness of breath is one of the most frequent symptoms. Heart failure can be treated with various types of medicine, but in severe heart failure so that sufficient circulation cannot be maintained, heart transplantation may be the only treatment. Shortage of transplant organs results in waiting time for transplantation. Therefore, an LVAD has been developed that can maintain adequate blood circulation as either temporary treatment before heart transplantation or as definitive treatment in patients who cannot undergo regular heart transplantation. The LVAD is implanted in the thorax and helps pump blood from the left ventricle into the aorta. The LVAD is located on top of the left hemidiaphragm and can therefore inhibit the movement of the diaphragm. Thereby, the LVAD can give rise to shortness of breath, and in patients who have concurrent heart failure, it can thus be difficult to assess whether shortness of breath is due to heart failure or reduced diaphragm function. Treatment that these conditions are different.

Heart transplantation entails a complete replacement of the heart. Due to the close relationship with the phrenic nerve, this can be damaged during the operation and thus result in reduced diaphragm function.

Some diseases, e.g. Cancer of the lung, mediastinum and esophagus requires thoracic surgery. Nerves to the diaphragm can be damaged during the operation and thereby cause reduced diaphragm function, which can lead to shortness of breath. Pleural effusion is common after thoracic surgery and also manifests as shortness of breath. In addition, patients often have other competing diseases such as chronic obstructive pulmonary

disease (COPD) or heart failure, which can also cause shortness of breath. This results in complex diagnostic conditions and complicates the investigation of shortness of breath after thoracic surgery.

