## STUDY 2:

## PLANNED HEART TRANSPLANTATION:

Patients who are registered on the heart transplant list, etc. imminent heart transplant, will be informed about the project at the preliminary examination for this treatment or regular check-up prior to heart transplantation, which takes place in a private room. Both oral and written information is given here. After being put on the waiting list, patients will be informed and written consent will then be secured. Relatively close to this date, there will be the possibility of a follow-up interview with the possibility of the participation of co-chairs. The reflection time will thus be >1 day.

Registration for a heart transplant: Informed by doctor. Delivery of participant information

At least 2 days after the prescription: Additional information if desired, with co-owners. Completing informed consent.

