#### STUDY 2:

Participants act as their own controls and before/after differences are analyzed with or univariate ANOVA for repeated measurements.

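### In Study 2 the heart-transplant baseline is taken near listing, so the before/after change cannot be attributed to transplantation alone

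*Combined protocol and SAP*

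**What the plan says.** The Surveys section for Study 2 sets the scan times. For the device group it reads "LVAD implantation: 1) the day before surgery, 2) 14 days after surgery and 3) 3 months after surgery", and the two cancer groups also have a baseline one day before the operation. Heart-transplant patients are the exception: their first examination is "in close relation to the write-up on the heart transplant list", followed by "2) 14 days after the operation and 3) 3 months after the operation". The layman's summary repeats this schedule. The recruitment section is consistent with it: "After being put on the waiting list, patients will be informed and written consent will then be secured".

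The background for Study 2 states "Shortage of transplant organs results in waiting time for transplantation" and describes the LVAD as "either temporary treatment before heart transplantation or as definitive treatment". It adds that the device lies on the left hemidiaphragm and can restrict its movement.

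One of the stated aims is to find out whether heart transplantation affects diaphragm function. The analysis section for Study 2 says "Participants act as their own controls" and names a repeated-measures ANOVA. It has no term for the length of the wait or for an LVAD implanted during it, and it does not say whether LVAD and transplant patients are analysed together. No section sets a maximum scan-to-transplant interval or a repeat scan before the operation. The eligibility criteria do not exclude patients who receive an LVAD while listed.

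**The concern.** Using patients as their own controls identifies the effect of an operation only if little else changes between the two scans. That is a reasonable assumption when the baseline is one day before surgery. It is much weaker when the baseline is at listing and the operation follows a wait of unstated length in patients with severe heart failure, some of whom may have a second chest operation in the meantime.

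At stake is what the transplant arm can say about its aim. Decline during the wait would look like harm from the transplant, and improvement during the wait would hide such harm. There is no untransplanted comparison group to tell these apart. If the interval and any interim LVAD are not recorded, nobody can later judge how far the result may be affected.

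**Working it through.** **Inputs from the plan.** The Study 2 strength calculation for lung/oesophageal patients gives mean M-mode movement 6.65 mm, SD 2.38, a 20% change, power 0.9, alpha 0.05 and 36 patients. The LVAD/transplant group is approximately 40 patients combined over 2 years, with no power calculation.

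**Assumptions, not in the documents.** 20 transplant patients (half of 40, with 10 and 30 shown as a range); mean drift of 5%, 10% or 15% during the wait; the cancer-group mean and SD apply to cardiac patients.

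**Step 1: reproduce the plan's figure.** The target difference is 0.20 × 6.65 = 1.33 mm. The normal approximation gives n = ((1.960 + 1.282) × 2.38 / 1.33)² = 33.6, so 34. The exact two-sided paired t-test has power 0.895 at n = 35 and 0.903 at n = 36. The plan's 36 is therefore reproduced with 2.38 acting as the SD of the within-patient change, and the same reading is used below.

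**Step 2: what the comparison estimates.** For a transplant patient, observed change = change during the wait (D) + effect of any LVAD operation in between (L) + effect of the transplant (T). The planned analysis estimates the mean of D + L + T. With T = 0 it estimates the mean of D + L.

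**Step 3: illustration with T = 0 and drift only.** This uses a two-sided paired t-test of baseline against one follow-up, a simplification of the planned ANOVA. The noncentrality is drift × √n / 2.38. For n = 20 and 10% drift it is 0.665 × 4.472 / 2.38 = 1.25, against a critical t of 2.093 on 19 degrees of freedom. The chance of p<0.05 is:

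| Mean drift | mm | n = 10 | n = 20 | n = 30 |
|---|---|---|---|---|
| 5% | 0.33 | 7% | 9% | 12% |
| 10% | 0.67 | 12% | 22% | 32% |
| 15% | 1.00 | 22% | 43% | 60% |

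**Step 4: the opposite direction.** With 20 patients, a true 20% fall from transplantation (1.33 mm) would be detected with probability 66%. If movement had improved by 10% (0.665 mm) during the wait, the observed fall would be 1.33 − 0.665 = 0.665 mm, and the probability drops to 22%.

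**Step 5: an interim LVAD operation alone.** Suppose the implant operation left a lasting 20% reduction in a fraction f of transplant patients. The mean shift is f × 1.33 mm: 0.13, 0.33 or 0.67 mm for f = 10%, 25% or 50%. Holding the SD at 2.38 and n at 20, the chance of p<0.05 is about 6%, 9% or 22%.

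**Step 6: which endpoints are exposed.** The Study 2 primary endpoint is M-mode movement on the right side only, and the background places the LVAD on the left. The device's direct mechanical effect therefore bears mainly on the secondary endpoints, which are not limited to the right side. Drift during the wait, and effects of the implant operation itself, can still reach the primary endpoint.

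**The case against.** The best case for the plan is feasibility. The transplant group was given its own timing rule, recruitment and consent are tied to listing, and examinations are placed at visits that occur anyway. The group is described as pragmatic and has no power calculation, within an observational study. A scan one day before an unscheduled operation may not be possible. This explains the choice, and nothing here asks for such a scan, but it does not change what the comparison estimates.

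Three stronger readings are tempting, and the objections to them stand.

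- A reader might infer that a bridging LVAD's inhibition of the diaphragm is charged to the transplant. The background describes transplantation as complete replacement of the heart and the bridging device as temporary, which suggests that the device is gone by the post-transplant scans. If it was implanted after the listing scan, its mechanical effect would then be in neither measurement. Only a lasting effect of the implant operation would remain.
- A reader might infer that taking the latest post-LVAD scan as baseline repairs the comparison. That could put the device's inhibition into the before value, so that its release counts as improvement from transplantation. For patients without an LVAD in the study, the last scan before transplant is still the listing scan, so redefining the baseline changes nothing. The documents do not support a claim that most of the bias can be removed.
- A reader might apply the drift to all 40 patients, which gives 41% or 73% false positives at 10% or 15% drift. Those figures do not describe this study: the 40 includes LVAD patients, whose baseline is one day before surgery.

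**Conclusion.** The point holds as a limit on attribution. Because the transplant baseline is taken near listing, the before/after change covers the wait, any LVAD operation in between and the transplant, and cannot be read as the effect of transplantation alone. The other three groups do not share this problem.

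Neither direction nor size follows from the documents, which give no waiting time, bridging rate or drift. In particular, they do not show that patients deteriorate while listed. The 9%, 22% and 43% for 20 patients show how sensitive the comparison would be under the stated assumptions. They are not estimates for this study. The point concerns one of the operations named in the aim and leaves the rest of Study 2 untouched.

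**What to change.** In the Surveys and Data analysis sections for Study 2:

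- Analyse transplant patients separately from LVAD patients.
- Record the interval from baseline scan to transplantation, and any LVAD implanted in that interval.
- Report change against the interval, with the interval as a covariate. Label this exploratory: with so few patients and no untransplanted comparison, separating drift from surgery means extrapolating to a zero wait.
- Add a sensitivity analysis that excludes patients given an LVAD after the baseline scan. Using a post-LVAD scan as baseline should be at most a further sensitivity analysis, not the primary rule.
- Word the conclusion as change from listing to after transplant.

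The cost is protocol wording and two recorded variables, with no added visit. The downside is smaller numbers in the sensitivity analysis. These steps make the limitation visible and partly testable, but they do not remove drift in patients whose only pre-operative scan is the one near listing. This is a cheap improvement.

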#### PULMONARY FUNCTION TEST:

Lung function testing takes place by having the patient blow as hard as they can into a tube. Various endpoints are then measured automatically by a machine. 3 inhalations are made per study, of which the values from the best are used.

#### **INSPIRATION'S PRINT:**

Inspiratory pressure is measured with an electronic manometer. It consists of a mouthpiece that you breathe into and which automatically measures the pressure.

## ULTRASOUND EXAMINATIONS:

The participants are examined in a standing/sitting position with ultrasound in the mid-axillary line with the liver/spleen as a reference point on the right and left side. A movie clip is saved for later analysis.

Diaphragm movement is measured in 3 different ways: M-mode, Area method and B-mode. [1] [2] [3] [4] Diaphragm thickening fraction is measured in 1 way. [5]

Normal and deep breathing is carried out.

#### TRANSLUCENT:

Performed only in study 1. Film clips of the movement of the diaphragm during X-ray translucency are recorded.

Transillumination, inspiratory pressure measurement and ultrasound examination are carried out simultaneously. Normal and deep breathing is carried out.

## ENDPOINTS

#### STUDY 1:

Diaphragm movement and thickening fraction compared to the cranial movement of the diaphragm as measured by translucency (gold standard) for the following measures:

Primary endpoint:

• Movement of the right hemidiaphragm: 1. M-mode method.

## Secondary endpoints

- o Movement of the right hemidiaphragm by 1. Area method & 2. B-mode.
- Thickening fraction of the right hemidiaphragm: 1. B-mode.
- o Inspiratory pressure

The above is assessed by correlations and Bland-Altman analysis where relevant.

Correlations are made between lung function (FEV1, FVC, FRC) and ultrasound measurement of diaphragm function (see above) as well as diaphragm function measured by transillumination.

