#### PARTICIPANTS

## STUDY 1:

Participants are divided into 3 categories: 1/3 healthy, 1/3 lung medicine patients and 1/3 patients who have had a heart transplant or LVAD implanted. Everyone over 50 years.

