## STRENGTH CALCULATION

## STUDY 1:

There is no data available for test-retest variance within ultrasound methods or fluoroscopy. It is therefore not possible to make a power calculation of how the spread in the comparison of two methods will be (Limits of agreement with Bland-Altman analysis). The starting point is therefore the bias (absolute difference in mean value) between an ultrasound method (m-mode method) and transillumination. As this is a methodological study, greater requirements are set than in study 2 (see below) for which bias can be detected. Assuming equal variation for the two methods, a detection of bias of 10% (SD 36%, own data for M-mode method) will require 92 participants (power 0.8 and alpha 0.05). Due to uncertainty about SD on the screening method, it is desired to include 100 participants.

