## SUMMARY OF DESIRED NUMBER OF INCLUDED PATIENTS

## STUDY 1:

We want 100 patients (34 healthy, 33 pulmonary medicine patients and 33 patients who have had a heart transplant/LVAD) included, distributed equally between the 3 groups to compensate for drop-outs and increase power.

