#### DATA REGISTRATION

The following demographic data are recorded: sex, height, weight, age and comorbidity. Demographic data is obtained from Region Midt's EPR system as well as anamnestic data. Consent to the trial gives the trial group and any accounting body the right to obtain information in the patient record regarding conditions that are relevant to the trial and for control purposes.

Data is registered in Case-Report-Form in RedCAP, which is administered by Aarhus University. The Danish Data Protection Authority's rules are followed and all personally identifiable data is deleted at the end of the study.

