## DATA ANALYSIS

#### STUDY 1:

Movement is measured continuously (centimeters or square centimeters) and calculated as a mean with standard deviation for the various ultrasound measurements. Correlation between diaphragm movement and sex, age, BMI is analyzed with multivariable analysis of variance, MANOVA.

The different measurement methods are compared individually with the golden standard with the paired T-test (Wilcocon's test if non-parametric). The 0 hypothesis is that there is no difference between the index method and the golden standard. Data is also depicted with a Bland-Altman plot and correlation between the index test and the golden standard.

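### Study 1's correlations of FEV1, FVC and FRC with diaphragm movement name no adjustment for sex, age or height, so a shared dependence on these could pass for a direct link

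*Combined protocol and SAP*

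**What the plan says.** The analysis appears under Endpoints, Study 1, Secondary endpoints: "Correlations are made between lung function (FEV1, FVC, FRC) and ultrasound measurement of diaphragm function (see above"). The sentence goes on to include diaphragm function measured by fluoroscopy. It names no covariates, no stratification by participant group, and no scale for lung function (absolute or percent of predicted).

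Data analysis, Study 1, fixes the scale of movement: "Movement is measured continuously (centimeters or square centimeters) and calculated as a mean with standard deviation for the various ultrasound measurements". The same section uses sex and age once: "Correlation between diaphragm movement and sex, age, BMI is analyzed with multivariable analysis of variance, MANOVA". Lung function is not part of that analysis.

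Under Data registration, the adjusting variables are collected: "The following demographic data are recorded: sex, height, weight, age and comorbidity".

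Participants, Study 1, describes a deliberately mixed sample: "Participants are divided into 3 categories: 1/3 healthy, 1/3 lung medicine patients and 1/3 patients who have had a heart transplant or LVAD implanted". The age restriction is "Everyone over 50 years". The target under Summary of desired number of included patients is "We want 100 patients (34 healthy, 33 pulmonary medicine patients and 33 patients who have had a heart transplant/LVAD) included".

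**The concern.** Two measurements that both depend on a third quantity are correlated even when neither has anything to do with the other. Sex, age and stature are plausible third quantities for lung function and for the distance the diaphragm travels. The planned correlations do nothing to separate such a shared influence from a direct link.

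The MANOVA does not fill the gap. It describes how movement varies with sex, age and BMI, but it does not remove those factors from a correlation calculated elsewhere. Height enters it only through BMI, which is weight divided by height squared and does not stand in for stature.

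The three-group sample offers a second route. If the groups differ in mean lung function and in mean movement, the pooled correlation reflects those differences even when there is no association within any group.

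What is at stake is the reading of a secondary result. A positive coefficient could be taken to show that an ultrasound measure tracks ventilatory function, when it partly reflects who is tall, male, younger or healthy.

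**Working it through.** **Is there a figure to reproduce?** No. The documents give no sample size, power or expected value for these correlations. The one Study 1 calculation concerns another quantity, the paired bias of M-mode against fluoroscopy ("a detection of bias of 10% (SD 36%, own data for M-mode method) will require 92 participants (power 0.8 and alpha 0.05"), and it is not used here.

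**Inputs**
- n = 100, the Study 1 target.
- Two-sided level 0.05. This is my assumption for the lung-function correlations, because the plan attaches no test to them.
- a = correlation of lung function with a single body-size/sex/age factor, and b = correlation of movement with the same factor. The documents give neither, so both are assumed and shown over a range.

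**Formulas**
- With no direct link, the induced correlation is r = a × b.
- The smallest correlation that is nominally significant is t/√(n − 2 + t²). With n = 100 and t = 1.984 this is 1.984/√(98 + 3.94) = 0.197. In a single group of 33 it is 0.344.
- Probability of nominal significance by Fisher's z: with d = atanh(r) × √(n − 3) and √97 = 9.849, it is Φ(d − 1.96) + Φ(−d − 1.96).

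**Equal links, n = 100, no direct association**

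| a = b | r = a × b | d | Probability of p < 0.05 |
|---|---|---|---|
| 0.3 | 0.09 | 0.89 | 0.14 |
| 0.4 | 0.16 | 1.59 | 0.36 |
| 0.5 | 0.25 | 2.52 | 0.71 |
| 0.6 | 0.36 | 3.71 | 0.96 |

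**Unequal links.** This is a second assumed range, with lung function tied more closely to the factor (a = 0.5 to 0.8) than movement is (b = 0.1 to 0.5). The probability runs from 0.08 (a = 0.5, b = 0.1, r = 0.05) to 0.99 (a = 0.8, b = 0.5, r = 0.40). Mid-range values are 0.22 (0.6 and 0.2), 0.56 (0.7 and 0.3) and 0.81 (0.7 and 0.4).

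**Does adjustment cure it?** A simulation with one common factor, n = 100 and 20,000 runs per row gives:

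| a | b | Unadjusted | Partial |
|---|---|---|---|
| 0.6 | 0.1 | 9.3% | 4.8% |
| 0.6 | 0.2 | 22.5% | 5.1% |
| 0.7 | 0.3 | 56.4% | 4.9% |
| 0.7 | 0.4 | 81.1% | 5.0% |
| 0.8 | 0.3 | 67.9% | 5.0% |

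The partial correlation holds its nominal level when the shared factor is measured and adjusted for.

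**Price of adjustment.** Sex, age and height use three degrees of freedom, leaving 95 instead of 98. The threshold moves from 0.197 to 1.985/√(95 + 3.94) = 0.200. Adding the three-level group uses two more, for a total of five out of 100.

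**The case against.** The strongest reply is that the stronger form of this point goes beyond the text. A reader might infer that the plan ignores sex and age, that these variables are known to drive both measures, and that lung function will be analysed in litres. The documents support none of this. Sex, age and BMI are examined against movement, though separately. Planning to examine a relation is not asserting that it exists. The scale of lung function is simply not stated, so percent-predicted values are not excluded.

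A reader might also infer that the trial will claim that diaphragm movement determines lung function, or will rank the ultrasound methods by these coefficients. No hypothesis, threshold or causal reading is attached to them. The aim is precision against X-ray, and the case for replacing fluoroscopy rests on agreement with fluoroscopy. Because all methods are applied to the same people, confounding would distort a ranking only if body size affected the methods differently, and nothing here shows that it does.

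Three further limits are fair. Thickening fraction is a ratio and is less exposed than a length or an area. Restricting Study 1 to people over 50 narrows the age variation. An unadjusted correlation is a legitimate description of how the two measures move together across this mix of participants, and adjusting for group turns the question into a within-group one, possibly removing disease-related variation that the design set out to include.

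All of this stands, and it limits the claim. It does not remove the gap: no adjustment is named, movement is in absolute units, and no other planned analysis separates a shared influence from a direct link.

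**Conclusion.** The point holds as a cheap improvement. As written, the plan gives no way to tell a direct association between lung function and diaphragm movement from one produced by sex, age, height or participant group.

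The size is conditional. With assumed links of 0.3 to 0.6 each, an induced correlation of 0.09 to 0.36 would be nominally significant at n = 100 with probability 0.14 to 0.96. Under the second assumed range this becomes 0.08 to 0.99, and at the weak end the excess over 0.05 is minor. These figures rest on a single common factor, no direct link, two-sided testing and full recruitment. They show what could happen, not what will.

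The effect is confined to a secondary analysis. The primary M-mode comparison with fluoroscopy, its sample size and the agreement analyses are untouched.

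**What to change.** In Endpoints, Study 1, and Data analysis, Study 1:

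1. State whether FEV1, FVC and FRC are analysed as absolute values or as percent of predicted. If percent of predicted, name the reference equations, which the documents do not give.
2. Keep the unadjusted correlations, labelled as descriptive.
3. Add partial correlations, or regressions, of each movement measure (each ultrasound method and fluoroscopy) with FEV1, FVC and FRC, adjusted for sex, age and height. Name these as the basis for interpretation. Use height itself, not BMI.
4. Show a further version also adjusted for participant group as a sensitivity analysis, and say that it answers a within-group question.

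The cost is three degrees of freedom out of 100, or five with group, and slightly more analysis work. No new data, visits or participants are needed.
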